7.7 Drug Abuse and Dependency

None known.

7.8 Other Clinically Relevant Information

The other clinically relevant information section of the DCSI documents safety observations or events that may be potentially relevant in the clinical management of subjects receiving tebentafusp. A reasonable possibility of a causal association with tebentafusp and the potentially medically important observations or events listed below (in Sections 7.8.1 to 7.8.4) has not been established, and, at this time, are not considered expected for the purpose of expedited reporting. Further characterization is ongoing.

7.8.1 Tumor Flare/Pain

Pain or inflammation at the site of known tumors has been reported in the tebentafusp development program and could be due to inflammation secondary to immune activation. Clinical manifestation may vary according to the anatomic location of the tumor. For example, serious and non-serious TEAEs of dyspnea, tachypnea, pleuritic effusion, and hypoxia have been reported. Patients should be managed symptomatically as indicated and IV corticosteroid therapy should be strongly considered in cases where symptoms persist or do not respond to initial medical therapy. In addition, evaluation and management of pain should be performed as clinically appropriate.

7.8.2 Elevated Pancreatic Enzymes

Increased amylase and lipase, including Grade 3 and Grade 4 elevations, have been observed following treatment with tebentafusp in the context of CRS and/or tumor flare as a transient phenomenon.

Among the 505 patients who received tebentafusp monotherapy across all studies (as of the DCO of 13 October 2021), TEAEs of lipase increased occurred in 50 (9.9%) patients (including 18 [3.6%] patients with Grade 3 or Grade 4 events) and amylase increased occurred in 22 (4.4%) patients (including 3 [0.6%] patients with Grade 3 or Grade 4 events). Most of the events of lipase increased and amylase increased were causally related to tebentafusp. None of these events were fatal or associated with Type 1 diabetes.

7.8.3 Lymphopenia

Monitoring of white cell counts revealed that lymphocytes in patients are trafficking post-treatment. In general, lymphocyte numbers increased in the circulation soon after infusion commenced and then dropped dramatically at approximately 24 hours, sometimes manifesting in laboratory values as Grade 1–4 lymphopenia. However, it is important to note that this trafficking of lymphocytes is a desired effect of tebentafusp. Tebentafusp is expected to activate T cells at sites where it binds the target gp100 peptide, thereby causing the release of a number of inflammatory mediators including chemokines. Chemokine release will trigger the trafficking of lymphocytes to the site of inflammation. In support of this, where serial biopsies have been sampled from patients, the infiltration of lymphocytes into skin and tumor 2 days after the first dose of tebentafusp was observed. The lymphopenia has been shown to be transient and self-resolving, with lymphocyte counts returning to baseline by Day 8. Rises in C-reactive protein levels have also been noted in a number of patients at the higher dose levels. Again, elevated C-reactive protein may be considered to be a related pharmacological mechanism of action of tebentafusp-mediated inflammation.

7.8.4 Ophthalmologic and Audiologic Toxicity

Prior to initiation of Phase 1 investigation of tebentafusp, the eye and ear were identified as potential target organs for toxicity, based on expression of the antigen in these target tissues. Across the tebentafusp development program to date, there have been no clinically significant TEAEs involving vision and/or hearing.

[figure not shown]
8. PHARMACEUTICAL INFORMATION

8.1 Study Agent

Tebentafusp is a 77 kDa bispecific protein with targeting and effector moieties which is manufactured in *E. coli* (Figure 1). The targeting portion of tebentafusp (TCR) functions to bind to the gp100 antigen as presented by MHC Class I on the surface of melanoma cells. These targeting TCRs are engineered versions of naturally occurring receptors found on the surface of T cells. In the natural situation, both diseased and healthy cells process cell proteins into peptide fragments and present these fragments at the cell surface via the Class I MHC. The system provides a means for the circulating cells of the immune system to recognize and attack diseased (or non-self) tissue. This particular function is performed by the T cell component of the immune system via the TCR.

The targeted gp100 peptide is presented by a subset of the population that express a specific variant of the MHC Class I complex known as HLA-A*02:01. This variant is carried by approximately 50% of the population in the Western World.²³ The gp100 protein is a 661 amino acid melanosomal membrane associated glycoprotein which is expressed in normal melanocytes and in the majority of melanoma tumors. The exact function of the protein is unknown, but it appears to be involved in melanosome maturation (Hoashi, 2005; Kawakami, 1997).^{24,25} The gp100 antigen has been, and continues to be, the target of a number of immunotherapy based melanoma clinical trials.

Figure 1: Tebentafusp structure and functional domains

Tebentafusp is a biologic with an effector and targeting end. The targeting end is an affinity enhanced, soluble TCR recognizing the gp100 antigen and the effector end is an anti-CD3 binding domain. The kinetic measurements were generated using soluble proteins and the surface plasma on resonance (BIAcore) method. The effector function (anti-CD3) works by binding and activating T cells via CD3. These T cells can be tumor-specific cells which are already resident in the tumor (tumor infiltrating lymphocytes) but circulating polyclonal T cells may also be activated as they traffic through the tumor as part of the normal blood supply. CD4+ and CD8+ T cells are both activated by tebentafusp triggering cytolytic activity associated with release of immune mediators — potentially resulting in a cascade of anti-tumor immune effector mechanisms — and T cell proliferation. Studies on CD8 T cell subtypes have shown that effector memory, central memory, and naïve cells all respond to tebentafusp stimulation as well as CD4+ T cells. Memory T cell activation following exposure to tebentafusp is rapid (PD effects seen within hours of exposure) and naïve cell activation can take a few days, which is consistent with the biology of these cell types.

8.2 Preparation and Administration

For all study medication administration and protocol-specified inpatient hospitalizations, a physician must be present at the site or immediately available to respond to emergencies during all administrations of all study medications. Critical care and resuscitation facilities should be immediately available.

Table 1: Tebentafusp dose and schedule

Study Treatments	Pharmaceutical Form and Route of	Potency and Packaging	Dose	Frequency and/or Regimen
------------------	----------------------------------	-----------------------	------	--------------------------

Administration				
Tebentafusp	Concentrate for solution for infusion (single use vials)	0.2 mg/mL	20 mcg C1D1; 30 mcg C1D8; 68 mcg C1D15 and subsequent doses	Every week: Days 1, 8, and 15 of 21-day cycle

Tebentafusp 0.2 mg/mL drug product for IV infusion will be provided as a sterile, refrigerated solution in individual glass vials, held at 2 to 8°C. Each glass vial will contain approximately 0.5 mL (extractable volume) with a concentration of 0.2 mg/mL. Each vial is designed for single use (single-dose) only and is not to be used to treat more than one patient.

The target duration of administration of tebentafusp is 15 to 20 minutes per infusion. The entire content of the IV bag must be infused using an infusion pump. The IV line must be flushed after the contents of the IV bag are fully administered according to institutional policy to ensure the full dose is administered. It must be documented if the line was not flushed.

Detailed dose preparation instructions will be provided in the study pharmacy manual and/or in the relevant pharmacy handling instructions.

8.3 Formulation, Packaging and Labelling

Tebentafusp drug product is presented as a sterile, concentrate for solution for infusion/injection. Tebentafusp is currently available in the following configuration: 0.2 mg/mL tebentafusp for IV infusion.

8.4 Availability

Tebentafusp will be supplied by Immunocore.

8.5 Agent Ordering

Tebentafusp will be distributed by Immunocore to sites. Please refer to the operations manual for more details and a drug order form.

8.6 Agent Accountability

Accountability and patient compliance will be assessed by maintaining adequate drug dispensing and return records. Compliance with individual patient dosing is assured as the drug is administered intravenously and recorded at the clinical site.

Accurate records must be kept for each study drug provided by the sponsor. The drug dispensing log must be kept current and contain the following information:

- documentation of drug shipments received from the sponsor (date received and quantity)

- disposition of unused study drug not dispensed to patient
- the identification of the patient to whom the study medication was dispensed
- the date(s) and quantity of the study medication dispensed to the patient

This inventory must be available for inspection by the Monitor. All supplies, including partially used or empty containers and copies of the dispensing & inventory logs, must be returned to SARC/Immunocore. Monitor at the end of the study, unless alternate destruction has been authorized by SARC/Immunocore or required by local or institutional regulations (Section 8.7).

8.7 Destruction of Tebentafusp

Local or institutional regulations may require immediate destruction of used investigational product for safety reasons e.g., cytotoxicity. In these cases, it may be acceptable for investigational site staff to destroy dispensed investigational product before a monitoring inspection provided that source document verification is performed on the remaining inventory and reconciled against the documentation of quantity shipped, dispensed, returned and destroyed. Written authorization must be obtained from the sponsor at study start up before destruction.

Written documentation of destruction must contain the following:

- Identity (batch numbers or patient numbers) of investigational product(s) destroyed
- Quantity of investigational product(s) destroyed
- Date of destruction (date discarded in designated hazardous container for destruction)
- Method of destruction (the site must provide the sponsor with documentation of their institutional policy and procedures for handling and disposing of hazardous drugs)
- Name and signature of responsible person (or company) who destroyed investigational products(s)

A list of the adverse events and potential risks associated with Study Agent can be found in Section 7.1.

9. CORRELATIVE/SPECIAL STUDIES

9.1 Laboratory Correlative Studies

Research Blood

Peripheral blood samples for research will be obtained at baseline, C2D1, C3D1, C5D1, C9D1, and EOT. At each research blood collection time point the following samples will be collected:

- 2x10ml of peripheral venous blood will be collected in EDTA tubes
- 2x10ml of peripheral venous blood will be collected in Streck tubes

Tumor Biopsies

Archival tissue may be requested from all patients at any time after informed consent has been obtained and prior to withdrawal of consent.

Tumor biopsies for research purposes will be done at baseline and week 6, where feasible. Biopsy at the time of progression for analysis of tumor microenvironment and for potential mechanisms of immune escape will be optional.

The same tumor site will be biopsied at each time point, if feasible. Cores will be obtained with 18-gauge needles where appropriate and be of at least 1 cm in length. The quality, viability, and tumor content of biopsies will be confirmed by the on-call clinical pathologist at the time of retrieval. The goal will be to extract up to 6 cores for paraffin embedding (FFPE).

9.1.1 Collection, Handling, and Shipment of Specimens

All biospecimens collected from patients enrolled in SARC045 will be kept at a SARC designated specimen bank. Samples will be transported in compliance with current regulatory guidelines for transport of biological specimens. Sample collection and processing will be conducted as described in the SARC Operations Manual provided to each participating site. Complete details for collection, handling and shipment of specimens will be provided in the Operations Manual.

9.2 Biomarker Analyses

9.2.1 Density of Immune Infiltrate and Immune Regulatory Biomarker Expression

Multiplex immunofluorescence will be used to assess the number and composition of immune infiltrates to define the immune cell subsets present within the tumor before and after exposure to tebentafusp. Immune checkpoint expression within the tumor and on immune cells before and after exposure to tebentafusp will also be determined.

9.2.2 Gene Expression Profiling

Tumor cores will be analyzed by RNA sequencing. Software tools will be utilized to generate and perform quality control on BAM files and to quantify gene expression, including deconvolution to quantify immune cell populations. Additional analyses will include hierarchical clustering on principal components, differential gene expression, and pathway enrichment analysis, all of which may stratify patients who benefit and those who do not benefit from tebentafusp therapy.

9.2.3 Peripheral Blood Analysis for ctDNA

ctDNA will be extracted from plasma and DNA isolated from plasma will be quantified and sequenced. Baseline quantity of ctDNA and the change in ctDNA across time will be correlated with clinical endpoints.

9.2.4 Other tests

Multi-omic analysis, such as whole genome sequencing, whole exome sequencing, single-cell sequencing, methylation profiling, spatial profiling, or other techniques may be utilized as needed to better understand the molecular profile of CCS samples and the impact of tebentafusp treatment on the tumor or peripheral blood.

10. STUDY EVALUATIONS AND STUDY CALENDAR

10.1 SCREENING STUDIES

10.1.2 Pre-screening

Patients with a diagnosis of unresectable or metastatic CCS who are considered for this study will first enter the pre-screening study phase. Patients will sign a pre-screening informed consent form and undergo HLA testing in a CLIA-certified laboratory. Patients who are HLA-A*02:01 will be eligible to sign consent for the interventional portion of this study and may initiate treatment after the screening phase. Patients who have had previous HLA typing via a CLIA-certified laboratory and have documentation demonstrating these results do not need to be re-tested. Patients who are HLA-ineligible will be offered the opportunity to participate in an observational study to track clinical outcomes with physician's choice of therapy.

- Patients should not sign the Main Study informed consent form and enter Screening until the results of the HLA testing are known and the patient has been confirmed to be eligible for the screening portion of the study

10.1.3 Screening

All aspects of the screening evaluation must be completed prior to entering the study, unless otherwise noted. The following must be completed within 28 days of starting treatment:

- Signed main study informed consent for study participation
- Confirmation of disease: documented presence of unresectable and/or locally advanced clear cell sarcoma, including pathologic confirmation and measurable disease by RECIST 1.1 with demonstration of progression within 6 months of registration (if not newly diagnosed)

- Full medical history including all active conditions
- Review of concomitant medications including any relevant prior medications taken
- Physical exam (including height and weight)
 - Note: height may be documented at any time prior to registration
- Vital signs (pulse, blood pressure, temperature, respiratory rate, and oxygen saturation).
- ECOG performance status
- Complete blood count with differential
- Comprehensive metabolic panel (sodium, potassium, chloride, bicarbonate, BUN, creatinine, glucose, total protein, albumin, total bilirubin, total protein, AST, ALT, alkaline phosphatase, calcium), magnesium, and phosphorus
- Amylase, lipase, CK, and LDH
- PT (or INR) and aPTT
- Thyroid function tests (TSH, T4 free, T3)
- HIV-1/2 antibody test, Hepatitis B surface antigen and core antibody, and Hepatitis C antibody, with reflex PCR test if positive
- Urinalysis (dipstick)
- Serum β -HCG or urine pregnancy test for women of child-bearing potential. If the urine test is positive or cannot be confirmed as negative, a serum pregnancy test is required
- 12-lead electrocardiogram (ECG)
- CT scan of the chest (with or without contrast), CT abdomen and pelvis (with contrast, unless contraindicated) or MRI abdomen pelvis (with and without contrast, unless contraindicated, and CT or MR of other known sites of disease, as clinically indicated
- Research biopsy
- Research blood collection

Laboratory and radiological assessments performed as part of standard of care prior to signing the informed consent may be used if performed within the screening time window (28 days prior to C1D1).

10.2 ON STUDY EVALUATIONS

All the assessments required as part of the study are indicated in the Study Calendar organized by visit date, with assessments required indicated with an “X” at the specific visits when they should be performed. Assessments required on C1D1 that are performed as part of the screening evaluations and within 72 hours prior to the first dose of study treatment do not need to be repeated on C1D1.

The following procedures will be performed during the treatment period:

C1D1

- Physical exam (short)
- Vital signs (Please see section 10.5)
- Relevant laboratory evaluations
 - Complete blood count with differential
 - Comprehensive metabolic panel (sodium, potassium, chloride, bicarbonate, BUN, creatinine, glucose, total protein, albumin, total bilirubin, total protein, AST, ALT, alkaline phosphatase, calcium), magnesium, and phosphorus
 - Amylase, lipase, CK, and LDH
 - PT (or INR) and aPTT
- Concomitant medications
- Administration of tebentafusp
- Recording of adverse events

CXD8, CXD15:

- Vital signs (Please see section 10.5)
- Concomitant medications
- Administration of tebentafusp
- Recording of adverse events

Cycle 2:

- Physical exam (short one, with weight)
- Vital signs (Please see section 10.5)
- Relevant laboratory evaluations
 - Complete blood count with differential
 - Comprehensive metabolic panel (sodium, potassium, chloride, bicarbonate, BUN, creatinine, glucose, total protein, albumin, total bilirubin, total protein, AST, ALT, alkaline phosphatase, calcium), magnesium, and phosphorus
 - Amylase, lipase, CK, and LDH
 - PT (or INR) and aPTT
- Concomitant medications
- Administration of tebentafusp
- Recording of adverse events
- Research blood

Cycle 3, etc.:

- Physical exam (short)

- Vital signs (pulse, blood pressure, temperature, respiratory rate)
- Relevant laboratory evaluations
 - Complete blood count with differential
 - Comprehensive metabolic panel (sodium, potassium, chloride, bicarbonate, BUN, creatinine, glucose, total protein, albumin, total bilirubin, total protein, AST, ALT, alkaline phosphatase, calcium), magnesium, and phosphorus
 - Amylase, lipase, CK, and LDH
- PT (or INR) and aPTT
- Concomitant medications
- Thyroid function tests (D1 of odd cycles)
- Recording of adverse events
- Administration of tebentafusp
- Recording of adverse events
- Serum β -HCG or urine pregnancy test for women of child-bearing potential. If the urine test is positive or cannot be confirmed as negative, a serum pregnancy test is required
- Radiographic assessment
 - Occurring every 6 weeks through 48 weeks, and then every 9 weeks thereafter
- Research blood (C3D1, C5D1, C9D1 only)
- Research biopsy (Cycle 3 only)

NOTE: All visits can be obtained ± 2 day of stated time point. Laboratory assessments may occur up to 2 days before infusion. Consecutive infusions of tebentafusp must be administered at least 5 days apart.

10.3 END OF TREATMENT EVALUATIONS

Final visit is to be performed at the time (or within 14 days after treatment stop date). End of treatment evaluations will include:

- Review of concomitant medications including any prior medications taken
- Physical exam (short)
- Vital signs (pulse, blood pressure, temperature, respiratory rate, and oxygen saturation).
- Relevant laboratory evaluations
 - Complete blood count with differential
 - Comprehensive metabolic panel (sodium, potassium, chloride, bicarbonate, BUN, creatinine, glucose, total protein, albumin, total bilirubin, total protein, AST, ALT, alkaline phosphatase, calcium), magnesium, and phosphorus

- Amylase, lipase, CK, and LDH
- PT (or INR) and aPTT
- Thyroid function tests (TSH, T4 free, T3)
- Urinalysis (dipstick)
- Serum β-HCG or urine pregnancy test for women of child-bearing potential. If the urine test is positive or cannot be confirmed as negative, a serum pregnancy test is required
- Research biopsy (if feasible)
 - EOT biopsy should be collected within 21 days of treatment stop or prior to starting next line of therapy.
- Research blood collection

Patients who complete study treatment should be followed for survival every 12 weeks until death, study withdrawal, or study end. Survival data can be collected by phone or EMR.

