5.3 Duration of Therapy

Treatment may continue until one of the following criteria applies:

- Disease progression as defined by RECIST v 1.1 unless criteria for treatment beyond initial PD is met (see Section 5.3.1)
- If continuing treatment beyond initial PD, then patients must discontinue study treatment once further PD warranting treatment discontinuation is met (see Section 5.3.1)
- Initiation of alternative anti-cancer therapy including another investigational agent
- Unacceptable toxicity as defined in Appendix B or any AE that, in the opinion of the investigator, contraindicates further dosing
- Withdrawal of consent from further treatment with investigational product by the patient or the investigator
- Patient is lost to follow-up
- Patient is determined to have met 1 or more of the exclusion criteria or failed to meet all of the inclusion criteria for study participation AND continuing to receive investigational product might constitute a safety risk. Patients who fall into this category and for whom continuation of treatment is not thought to pose a safety risk, in the opinion of the investigator, may continue to receive study treatment
- Pregnancy or intent to become pregnant

At the time patients discontinue study treatment, the EOT visit should be scheduled in the appropriate window of 14 days after the last dose was administered. At this visit, all of the assessments listed for the EOT visit will be performed. If the decision to withdraw the patient occurs at a regularly scheduled visit, that date of visit may become the EOT visit rather than having the patient return for an additional visit (safety follow-up will still continue for the full 30-day observation period). An EOT disposition document should be completed at the EOT visit, giving the date and reason for stopping the study treatment.

Patients who discontinue study treatment should NOT be considered withdrawn from the study. They should return for the assessments indicated in Section 11. If they fail to return for these assessments for unknown reasons, every effort (eg, telephone, email, and registered letter) should be made to contact them. If a patient discontinues study treatment, but continues study assessments, the patient remains on study until such time as he/she completes protocol criteria for ending study assessments. At that time, the reason for study completion should be documented.

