11.1.4.3 Evaluation of Best Overall Response

The best overall response is the best response recorded from the start of the treatment until disease progression/recurrence (taking as reference for progressive disease the smallest measurements recorded since the treatment started). The patient's best response assignment will depend on the achievement of both measurement and confirmation criteria.

For Patients with Measurable Disease (*i.e.*, Target Disease)

Target Lesions	Non-Target Lesions	New Lesions	Overall Response	Best Overall Response when Confirmation is Required*
CR	CR	No	CR	≥4 wks. Confirmation**
CR	Non-CR/Non-PD	No	PR	≥4 wks. Confirmation**
CR	Not evaluated	No	PR	
PR	Non-CR/Non-PD/not evaluated	No	PR	
SD	Non-CR/Non-PD/not evaluated	No	SD	Documented at least once ≥4 wks. from baseline**
PD	Any	Yes or No	PD	no prior SD, PR or CR
Any	PD***	Yes or No	PD	
Any	Any	Yes	PD	

* See RECIST 1.1 manuscript for further details on what is evidence of a new lesion.
** Only for non-randomized trials with response as primary endpoint.
*** In exceptional circumstances, unequivocal progression in non-target lesions may be accepted as disease progression.

Note: Patients with a global deterioration of health status requiring discontinuation of treatment without objective evidence of disease progression at that time should be reported as “*symptomatic deterioration*.” Every effort should be made to document the objective progression even after discontinuation of treatment.

For Patients with Non-Measurable Disease (*i.e.*, Non-Target Disease)

Non-Target Lesions	New Lesions	Overall Response
CR	No	CR
Non-CR/non-PD	No	Non-CR/non-PD*
Not all evaluated	No	not evaluated
Unequivocal PD	Yes or No	PD
Any	Yes	PD

* 'Non-CR/non-PD' is preferred over 'stable disease' for non-target disease since SD is increasingly used as an endpoint for assessment of efficacy in some trials so to assign this category when no lesions can be measured is not advised

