13. STATISTICAL CONSIDERATIONS

13.1 Study Design/Endpoints

This will be a multi-center open label phase II study of tebentafusp in patients with unresectable or metastatic CCS. CCS is an orphan disease with few efficacious systemic

treatment options and few standard of care treatment options in the unresectable or metastatic setting. This study will assess for a signal of efficacy of a novel immunotherapeutic agent (tebentafusp) in the HLA-A*02:01-positive patients and simultaneously prospectively measure real-world outcomes in the HLA-A*02:01-negative patients.

The primary endpoint is to estimate PFS rate at 24 weeks, as determined by RECIST 1.1. In the CREATE trial (one of the few prospective clinical trials in this disease), the PFS rate at 6 months (PFS₆) for patients with advanced CCS treated with crizotinib was approximately 25%.⁹ In other prospective and retrospective studies of alternative systemic therapies, the median PFS was between 2 and 3 months and the PFS₆ was not reported.^{6,8,32}

Van Glabbeke and colleagues³³ have previously described appropriate thresholds for PFS₆ in the design of phase II studies in soft tissue sarcoma patients refractory to first-line treatment. Based on historical controls, they conclude a PFS₆ of 8% is not promising and PFS₆ of 14% to be promising.³³ Based on all of the above, we believe PFS₆ is an appropriate and meaningful clinical endpoint in this patient population. We will consider a 10% PFS₆ as not promising and 30% to be promising.

Simon's two-stage minimax design³⁴ will be used. The null hypothesis that the true PFS rate at 24 weeks is 10% will be tested against a one-sided alternative that it is 30%. In the first stage, 13 patients will be accrued. If ≤ 1 of the first 13 patients enrolled is progression-free at 24 weeks, the protocol will stop enrolling patients due to futility. Otherwise, 10 additional patients will be accrued for a total of 23 patients treated. The study will be claimed positive if 5 or more of 23 patients are progression-free at 24 weeks. This design yields a one-sided type I error rate of 0.1 and power of 0.84.

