All patients who have received at least one dose of study therapy will be assessable for safety. Patients evaluable for efficacy analysis will include all patients treated with tebentafusp who are assessable for response. Patients who have no assessment of response post-baseline will not be considered evaluable for response unless they missed the assessment due to progression of disease or death, in which case they will be considered non-responders for that time point. Patients with at least one post-baseline assessment who are not assessed at 24 weeks for reasons other than progression of disease, death, will be evaluated based on their last imaging assessment. For example, patients with excessive toxicity will be censored at the date of their most recent disease evaluation prior to receiving any future systemic treatment regimens. Patients who are not evaluable (excluding those who died, had progression of disease, stopped study treatment due to treatment-related toxicity, or those with at least one post-baseline assessment) may be replaced.

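### The protocol contradicts itself on whether tumour imaging continues after tebentafusp is stopped without progression, and its calendar would drop the scans behind the 24-week endpoint

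*Protocol*

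**What the plan says.** **Passages that point to continued imaging.** Section 5.3 says that stopping treatment is not withdrawal from the study, and of these patients: "They should return for the assessments indicated in Section 11". Section 11.1 sets re-evaluation for response every 6 weeks. Section 11.1.4.3, in its note on symptomatic deterioration, adds: "Every effort should be made to document the objective progression even after discontinuation of treatment".

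**Passages that point to no further imaging.** Section 10.2 opens by saying that all required assessments are in the Study Calendar, and it lists scans among the procedures of the treatment period. Section 10.3 lists examination, laboratory tests, research biopsy and research blood at end of treatment, but no scan, and then says: "Patients who complete study treatment should be followed for survival every 12 weeks until death, study withdrawal, or study end". Those survival data may come by phone or from the medical record. In the calendar the radiographic row is empty under EOT and Follow-up, and Follow-up holds only the OS assessment. Section 5.4 and calendar footnote 10 also name only survival follow-up.

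**The calendar cell.** For Cycle 3 onward the radiographic row reads q9weeks. Its own footnote 6, the synopsis, section 2.4 and section 10.2 all give every 6 weeks through week 48 and every 9 weeks after that. Section 11.1 gives every 6 weeks.

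**The analysis that depends on these scans.** Section 13.1 stops for futility under this rule: "If ≤ 1 of the first 13 patients enrolled is progression-free at 24 weeks". Its final rule is: "The study will be claimed positive if 5 or more of 23 patients are progression-free at 24 weeks". When the 24-week assessment is missing for a reason other than progression or death, it uses the last imaging assessment. As an example, it censors patients with excessive toxicity at their last disease evaluation "prior to receiving any future systemic treatment regimens".

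**The concern.** A patient can stop tebentafusp before week 24 for toxicity, by choice or at the investigator's discretion while still free of RECIST progression. Such a patient is alive and contactable, and status at week 24 can be observed only by a scan. If the site works from the calendar, that scan is not scheduled. No later analysis rule can recover it. PFS and duration of response are also censored early in these patients.

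The loss is unlikely to be random, because patients who stop for toxicity or decline may differ in prognosis from those who stay on treatment. The decision rule works on small counts (1 against 2 of 13, and 4 against 5 of 23), so a few unobserved outcomes can matter when the count is near a cut-off.

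**Working it through.** **1. Which instruction would a site follow?** The route to continued imaging runs from 5.3 through a cross-reference to Section 11. That pointer may be out of date: Section 5 (Screening and Treatment) also cites Section 11.0 for the timing of required assessments, yet that timing is in Section 10. If 5.3 means Section 10, it leads to 10.3 and the calendar, which hold no scan. If it means Section 11 as printed, it leads to 6-weekly re-evaluation. Section 11.1 does not mention patients off treatment or the change to 9-weekly scans after week 48. The sentence in 11.1.4.3 asks for effort and sets no schedule. The two sets of passages cannot both govern.

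**2. The q9weeks cell.** Section 5 anchors scans to C1D1 with a window of ±7 days.
- Every 6 weeks: 6, 12, 18, 24. Week 24 is covered.
- Every 9 weeks: 9, 18, 27. The windows are weeks 17–19 and 26–28, so week 24 is missed.

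If a site counted 9 weeks from Cycle 3 Day 1 instead (2 × 21 days = week 6), scans would fall at weeks 6, 15 and 24. The cell misses week 24 under the protocol's own C1D1 reference, not under every possible reading.

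**3. Reproducing the stated design.** Inputs from section 13.1: null rate 0.10, alternative 0.30, n1 = 13 (stop if ≤ 1), N = 23 (positive if ≥ 5). The formula is

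P(positive) = Σ over x = 2..13 of P[Bin(13, p) = x] × P[Bin(10, p) ≥ max(0, 5 − x)].

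- p = 0.30: 0.844. The stated power of 0.84 is reproduced.
- p = 0.10: 0.068. The stated 0.1 fits as a nominal ceiling.

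**4. How many patients?** The only usable stopping rate is 2%, for treatment-related adverse events in the uveal melanoma trial (sections 2.2 and 5.1.2). Expected number: 23 × 0.02 = 0.46. Chance of at least one: 1 − 0.98²³ = 0.37. At an assumed 10%: 23 × 0.10 = 2.3, and 1 − 0.90²³ = 0.91.

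**5. Effect on the error rates.** Assumptions not in the protocol: PFS is exponential; a share d stops at week t for reasons unrelated to progression, with the last scan at t. Section 13.1 does not settle how a patient progression-free at that last scan enters the binary count, since using the last image and censoring are different things. Both extremes are therefore shown.

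- Counted as a success, the null rate becomes (1 − d) × 0.10 + d × 0.10^(t/24). For d = 2%, t = 6: 0.098 + 0.02 × 0.562 = 0.109.
- Counted as a failure, the alternative rate becomes (1 − d) × 0.30. For d = 2%: 0.294.

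Putting these rates into the formula in step 3 gives:

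| d | Type I error, last scan = success (t = 18 to t = 6) | Power, stop = failure |
|---|---|---|
| 0 (scans continue) | 0.068 | 0.844 |
| 2% (protocol) | 0.072 to 0.092 | 0.829 |
| 5% (assumed) | 0.078 to 0.135 | 0.806 |
| 10% (assumed) | 0.088 to 0.225 | 0.761 |

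**The case against.** A reader of the calendar might infer that no tumour scan at all is scheduled after treatment stops and that 24-week status is never observed in these patients. The protocol does not support that. Section 5.3 distinguishes stopping treatment from leaving the study, tells these patients to return, and describes a patient who stops treatment but continues study assessments. That is hard to read as survival contact alone. Read literally, its pointer to Section 11 reaches a 6-weekly interval. Section 5 says scans do not move with treatment delays, footnote 6 carries no on-treatment limit, and section 11.1.4.3 covers symptomatic deterioration. Sections 10.3 and 5.4 set a survival interval and do not say that imaging ends. This part of the objection stands: the defect is a contradiction, not an absence of follow-up imaging.

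A reader might also infer that the design's error rates are lost. At 2% they are not: type I error stays below the nominal 0.1 and power falls by 0.015. Being sensitive near a cut-off is common to all designs of this kind.

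The q9weeks cell can fairly be called a labelling slip about on-treatment scans, since its footnote corrects it. It is still a printed contradiction in the document that sites work from.

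Nor can it be said that the date of the next therapy goes uncollected. The eCRFs are not shown, section 4.1 promises capture of endpoint data, and 5.3 makes alternative therapy a stopping reason recorded at EOT. What can be said is that no scheduled item names a start date falling after EOT.

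The objection does not remove the statement in 10.2 that all required assessments are in the calendar, where the EOT and Follow-up columns hold no scan.

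**Conclusion.** The concern holds as an internal contradiction. Sections 5.3, 11.1 and 11.1.4.3 intend tumour assessment to continue after tebentafusp is stopped. Sections 10.2, 10.3 and 5.4 and the Study Calendar do not provide for it. A site following the calendar would leave the primary endpoint unobserved in patients who stop before week 24 without progression, and shorten their PFS and duration of response. The q9weeks cell is a second, separate contradiction in the same calendar row.

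The likely size is modest: about half a patient of 23 at the protocol's 2%. That figure comes from another disease and covers only related adverse events. It leaves out patient choice, investigator discretion and symptomatic deterioration, so the total share could be higher, but the protocol gives no figure for it. Results at 5% and 10% are assumptions, as are the exponential model and stopping unrelated to prognosis. The highest type I error shown, 0.225, needs a 10% share, stops at week 6, and every such patient counted as a success. The case for acting rests less on size than on the fact that a scan not taken cannot be restored at analysis.

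**What to change.** Reconcile the passages in one amendment:

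1. In section 10.3 and the calendar's Follow-up column, state that patients who stop tebentafusp without RECIST 1.1 progression continue RECIST imaging on the C1D1-based schedule until progression, new anti-cancer therapy, death or withdrawal of consent.
2. Correct the cross-reference in 5.3, and the matching one in Section 5, so that both lead to that schedule.
3. Change the q9weeks cell to agree with footnote 6.
4. Record the start date of the first subsequent anti-cancer therapy at EOT and at each 12-weekly survival contact, because section 13.1 censors by it.

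The cost is a change to one calendar row and a few sentences, some extra scans in the few patients concerned, and one data field. If the scans are obtained whatever the treatment status, the design keeps its exact figures of 0.068 and 0.844.
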